#### Cohort 1 (N = 3 to 6)

• 160 mg AFM24 i.v. qw + atezolizumab 840 mg i.v. q2w

#### Cohort 2 (N= 3 to 6)

Cohort 2: AFM24 i.v. qw (at dose to be based on the data from AFM24-101 in conjunction with the safety and available PK data emerging from this study, as determined by the SRC)
 + atezolizumab 840 mg i.v. q2w

#### Cohort 3 (N= 3 to 6)

 AFM24 i.v. qw (at dose to be based on the data from AFM24-101 in conjunction with the safety and available PK data emerging from this study, as determined by the SRC) + atezolizumab 840 mg i.v. q2w

Depending on the emerging safety and PK data from the ongoing AFM24-101 study, and timing for initiation of this study, an alternate starting dose and additional dosing cohorts may be considered (see Section 2.4).

# 6.6. Expansion Phase (Phase 2a) Treatment Schedule

Patients who are determined eligible post evaluation for AFM24-hypersensitivity during the safety-lead in phase (Day -7 through Day -1) will receive the investigational treatment (AFM24 + atezolizumab) as per the following regimens, with the RP2D defined as 480 mg as described in Section 2.5:

- EXP-1 (*EGFR-WT* NSCLC): AFM24 i.v. qw or q2w at RP2D dose + Atezolizumab 840 mg i.v. q2w
- EXP-2 (gastric or GEJ adenocarcinoma): AFM24 i.v. qw or q2w at RP2D dose + Atezolizumab 840 mg i.v. q2w
- EXP-3 (Hepatocellular Carcinoma, Hepatobiliary-, or Pancreatic Adenocarcinoma): RP2D AFM24 i.v. qw or q2w at RP2D dose + Atezolizumab 840 mg i.v. q2w
- EXP-4 (advanced or metastatic NSCLC harboring a targetable EGFR kinase domain mutation): RP2D AFM24 i.v. qw or q2w at RP2D dose + Atezolizumab 840 mg i.v. q2w

If AFM24 is given on a q2w schedule the daily dose of AFM24 will not be higher than the highest daily dose that was tested in the phase 1 part of the study and was considered safe.

Additional treatment schedules of AFM24 administration (e.g., q2w) may be explored as part of the Phase 2a within or across cohorts.

## 6.7. Dose Interruptions, Delays, Modifications and Discontinuations

## **AFM24**

Treatment may be delayed for up to 3 weeks to allow sufficient time for recovery from treatment-related toxicities to baseline or Grade ≤1 (except for alopecia), except during the DLT observation period during the dose escalation phase (Phase 1). See Section 5.4.2 for criteria requiring permanent discontinuation of study treatment.

Dosing delays longer than > 3 weeks may be permitted in a case-by-case basis per the Investigator's judgement after consultation with the Medical Monitor. No dosing delays (including planned dosing delays such as elective surgery) will be allowed during the DLT observation period. Tumor assessments should continue as per protocol even if dosing is delayed.

If an AE occurs during the AFM24 infusion Safety Lead-in (D-7), and the dose is interrupted, the patient can restart upon recovery to baseline or Grade ≤1 within the same day. If the patient already received 80 mg of the prescribed dose of AFM24 on the day of dose interruption or cannot recover within the same day of the event, the rest of the dose should be omitted.

#### Weekly dosing schedule:

If the patient recovers from an AE and can continue study treatment within 72 hours of the planned dose, the patient should receive the delayed dose and continue treatment as per the original schedule, by not shifting any later doses. There should be at least 3 days between infusions before the patient receives the next dose. An example: if the patient has an AE on Cycle 1 Day 15 and recovers in time and can receive the missed dose by Cycle 1 Day 18, then the next dose for the patient would be on Cycle 1 Day 22.

If the patient does not recover from an AE within 72 hours the missed dose(s) should be skipped and the patient should receive the next dose as per original schedule. An example: a missed dose on Cycle 2 Day 1 and the patient recovered on Cycle 2 Day 9, the next dose for this patient is on Cycle 2 Day 15.

## Every-2-weeks dosing schedule:

If the patient recovers from an AE and is able to continue study drug within 1 week from the original scheduled dosing day then the patient should receive the delayed dose and continue treatment as per the original schedule, by not shifting any later doses. There should be at least 7 days without treatment before the patient receives the next dose. An example: if the patient has an AE on C1D1 and recovers in time and can receive the missed dose latest on C1D8, then the next dose for the patient is on C1D15.

If an AE happens during the AFM24 infusion, and the dose is interrupted, the patient can restart upon recovery to baseline or Grade  $\leq 1$  within the same day. If the patient already received  $\geq 75\%$  of the prescribed dose of AFM24 and 50% of atezolizumab that day at the time of the interruption or cannot recover within the same day of the event, the rest of the dose could be omitted.

Patients who experience a DLT during the DLT observation period must permanently discontinue the study drugs.

In addition, AFM24 re-challenge following a CTCAE Grade ≥3 IRR or CRS should be handled as the following and the Investigator should refer for details:

- Grade 3 IRR or CRS that are NOT responsive to symptomatic treatment (i.e., no improvement of IRR-related symptoms to Grade 2 or better within 6 hours with optimal medical management): AFM24 should be discontinued permanently.
- Grade 4 IRR or CRS in all phases: AFM24 should be discontinued permanently.

[figure not shown]
IRRs other than anaphylaxis responsive to symptomatic treatment (i.e., improvement to Grade 2 or better within 6 hours with optimal medical management):

- Restart if symptoms resolve to CTCAE Grade ≤1 or baseline only at the discretion of the investigator based on the clinical status of the patient.
- If re-challenge is considered, infuse the next AFM24 infusion with a >4-hour infusion time.

#### Dose Modification:

During the dose escalation phase (Phase 1), if a patient is tolerating AFM24 in combination with atezolizumab well (i.e., no drug-related Grade ≥2 toxicity) without evidence of disease progression following 2 cycles, the patient may, beginning with Cycle 3 or a subsequent cycle, have the dose increased to a dose that has already been established as tolerable by the SRC, and with the agreement of the SRC.

## **Atezolizumab**

Continuation of therapy on-study in the setting of discontinuation of one component (AFM24 or Atezolizumab) of the study therapy

If one component of the study therapy is permanently discontinued secondary to toxicity, then therapy with the other component may continue at the discretion of the investigator and the patient should remain on-study with full adherence to all protocol-related requirements, provided the patient continues to meet entry criteria and does not have evidence of disease progression.

## 6.8. Permitted and Restricted Concomitant Medications

## **6.8.1.** Acceptable Concomitant Medications

All treatments and supportive care that the Investigator considers necessary for a patient's welfare may be administered at the discretion of the Investigator in keeping with the standards of medical care of the study site except for the prohibited concomitant medications listed in Section 6.8.2. All concomitant medication will be recorded in the patient's medical records and in the eCRF including all prescription, over-the-counter, herbal supplements, and i.v. medications and fluids. If changes occur during the study period, documentation of drug dosage, frequency, route, and date needs to also be included in the eCRF.

All concomitant medications received from Screening to the Safety Follow-up visit should be recorded (see Schedule of Assessments [ ]). Concomitant medications administered after the Safety Follow-up visit should be recorded for SAEs which are considered related to study drug (Section 10).

#### 6.8.1.1. COVID-19 Vaccination

Various guidelines (e.g., NCCN Guidelines: Cancer and COVID-19 Vaccination [NCCN 2023] and MHRA Guidance on Coronavirus [COVID-19]) [MHRA 2022] have noted that COVID-19 vaccination should be prioritized for patients with cancer with the understanding that there are limited safety and efficacy data in this patient group. These guidelines also state:

- "Delay of vaccination until immunosuppressive therapy is reduced and/or based on immunophenotyping of T cell and B cell immunity can be considered."
- "Systemic corticosteroids and targeted agents are expected to blunt immune responses to vaccination."

This study utilizes a mandatory premedication regimen that contains corticosteroids (i.e., 20 mg of i.v. dexamethasone [or equivalent of long-lasting steroid dose]) for at least the duration of the first cycle (i.e., Cycle 1). Therefore, every effort should be made to vaccinate patients prior to being considered for this study based on the Investigator's risk/benefit analysis for each patient. If a patient receives the COVID-19 vaccination prior to study participation, the vaccine should be administered at least 2 weeks prior to Day -7 or at least 4 weeks prior to Day -7 for live attenuated vaccines.

For patients whose opportunity for COVID-19 vaccination arrives during the conduct of the study (i.e., ongoing patients in the study), the following should be noted:

• COVID-19 vaccination should be avoided during the DLT period or Cycle 1 of the study period.

- As stated in Section 6.2, Investigators may taper premedication with corticosteroids for those patients who do not experience IRR/CRS symptoms Grade >2 during the previous infusion starting with the third subsequent AFM24 infusion (C1D8 weekly schedule and C1D15 for q2w schedule).
- If the vaccination opportunity falls within the mandatory corticosteroid premedication
  period, there should be a consideration by the Investigator for holding or tapering the
  corticosteroid to prioritize vaccination on a case -by -case basis based on the risk/benefit
  analysis by the Investigator/treating MD.
- COVID-19 vaccination is not permitted on AFM24 dosing days. Vaccination should be administered at least 3 days before or 3 days after the AFM24 treatment administration day.
- It should be noted that no planned dose delays for study drugs are allowed during the DLT period (i.e., Cycle 1).

#### 6.8.2. Prohibited Concomitant Medications

Medications specifically prohibited in the exclusion criteria are not allowed during the ongoing study. If there is a clinical indication for any medication specifically prohibited during the study, discontinuation from study drug may be required. The Investigator should discuss any questions regarding this with the Sponsor. The final decision on any supportive therapy rests with the Investigator and/or the patient's primary physician. However, in such cases, the decision to continue the patient on study regimen drug requires the mutual agreement of the Investigator, Sponsor, and patient.

Apart from the exceptions listed in the inclusion/exclusion criteria, patients are prohibited from receiving the following therapies during the Screening (see Section 5.2) and Treatment Period of this study, with exception of the treatment of AEs occurring during the study:

Patients who, in the assessment by the Investigator, require the use of any of the aforementioned treatments for clinical management should be removed from the study. Patients may receive other medications that the Investigator deems to be medically necessary.

# 6.9. Blinding and Procedures for Unblinding the Study

This is an open-label study, and there are no procedures for blinding and unblinding.

# 6.10. Management of AFM24-Related Toxicities

Any DLT during Cycle 1 in the Phase 1 part: Permanently discontinue AFM24.

Please see for a summary of management of IRR/CRS, and other AFM24-related AEs.

IRRs: for detailed grading criteria and detailed guidance on management.

CRS: for detailed grading criteria and detailed guidance on management.

**Dermatological toxicities:** Investigators are asked to pay special attention to ALL dermatological toxicities and consult with a dermatologist if needed. In cases of Grade ≥3 skin toxicity, AFM24 treatment should be interrupted or postponed until the reaction resolves to Grade ≤1 or baseline. Patients should be asked to limit direct sunlight exposure and apply protective sun cream during treatment with AFM24. A rechallenge should be considered at the discretion of the Investigator but AFM24 should be permanently discontinued with a recurrence of Grade 3.

**Electrolyte abnormalities:** Consider withholding AFM24 for Grade ≥2 electrolyte abnormalities and resume when resolved. Replenish electrolytes as medically appropriate.

**Pulmonary symptoms:** In the event of acute onset or worsening of pulmonary symptoms, interrupt AFM24 therapy. Discontinue AFM24 therapy if interstitial lung disease is confirmed.

**Hepatotoxicity:** If severe (>CTCAE Grade 3) hepatic impairment develops for patient with / without liver metastasis, AFM24 should be discontinued permanently.

Gastrointestinal Perforation: Permanently discontinue AFM24 in patients who develop gastrointestinal perforation.

**Other:** For all CTCAE Grade 3 toxicities other than those that meet the definition of a DLT during Cycle 1 of the dose escalation (i.e., Phase 1) phase, and other than those described above, interrupt treatment with AFM24 until resolved to Grade ≤1 or baseline. If CTCAE Grade 3 toxicity recurs upon rechallenge or in case of CTCAE Grade 4 toxicity, permanently discontinue treatment.

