## **DLT** observation period:

In order to be considered evaluable for DLT, patients must meet the following criteria:

- receive  $\geq 75\%$  of their assigned AFM24 dose in Cycle 1 *and*
- receive  $\geq 50\%$  of their assigned atezolizumab dose in Cycle 1 and
- either complete the 28-day DLT observation period *or* have had a DLT within the first cycle of treatment.

Patients discontinuing the study after the safety lead-in phase will not be included in the DLT evaluation.

**Table 1:** Definition of Dose-Limiting Toxicity

Toxicity	Any of the following criteria		
Hematological a	≥CTCAE Grade 4 neutropenia (ANC<0.5×10  /L) lasting for longer than 4 consecutive day		
	Febrile neutropenia (ANC<1.0×10  /L of any duration accompanied by fever ≥38.5°C or systemic infection) that does not resolve within 48 hours after start of antibiotics		
	CTCAE Grade 3 thrombocytopenia (platelets 25 to <50×10  /L) associated with bleeding		
	CTCAE Grade 4 thrombocytopenia (platelets <25×10  /L)		
	≥CTCAE Grade 4 anemia that is considered to be treatment related		
Non- hematological	
 
Any ≥CTCAE Grade 3 AE including, but not limited to:
 
CTCAE Grade 3 infusion-related reaction/cytokine release syndrome not responsive to symptomatic treatment within 6 hours (i.e., no improvement to Grade 2 or better within 6 hours with optimal medical management)
 
CTCAE Grade 4 infusion-related reaction/cytokine release syndrome
 
QTcF prolongation (>500 msec) confirmed by 2 separate ECGs at least 6 hours apart or if associated with arrhythmias;
 
CTCAE Grade 3 hypertension for >14 consecutive days despite optimal antihypertension therapy;
 
CTCAE Grade 4 hypertension (any duration)
 
≥CTCAE Grade 3 total bilirubin (>3×ULN);
 
≥CTCAE Grade 3 ALT, AST, or alkaline phosphatase (>5×ULN) if not resolving to Grade 1 or baseline within 10 days;
 
≥CTCAE Grade 3 diarrhea for ≥72 hours despite optimal anti-diarrhea treatment
 
Any death at least possibly related to any study treatment
 
		
	Any other ≥CTCAE Grade 3 AE not listed above, except for the exceptions noted below		
Exceptions to DLT criteriab	Isolated laboratory changes of any grade without clinical sequelae or clinical significance except for those laboratory changes outlined above		

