on a regular basis. Based on the outcome of their review, the IDMC will provide recommendations to the Sponsor regarding study conduct or study procedures. The set-up and operational process for this IDMC will be described in a separate IDMC charter.

The following stopping rules for the expansion phase (Phase 2a) part of the study apply:

- ≥ 3 patients report the same AE occurring within 30 days of starting study treatment meeting the DLT criteria in the same expansion cohort or
- ≥ 3 patients reported the same SAE with at least possible relationship to the study treatment occurring within 30 days of starting study treatment within the same expansion cohort, or
- any death with at least possible relationship to the study treatment occurring within 30 days of starting study treatment, or
- ≥ 30% patients experiencing the same SAE with at least possible relationship to the study treatment occurring within 30 days of starting study treatment across expansion cohorts.

If at least 1 of the stopping rules is met, patient recruitment will be paused. Patients who are already receiving study treatment and are deriving clinical benefit may continue study treatment at the discretion of the Investigator. The ICF will be updated with the new safety information, and the patients will be reconsented once the ICF is approved and available. Following the stop of patient enrollment, a thorough investigation will be done jointly by the Sponsor and the IDMC. The study will continue only if the IDMC confirms a positive benefit/risk assessment of the study treatment. Following a positive assessment by the IDMC, a substantial amendment will be submitted to the regulatory authority, and enrolment can be restarted only after approval by the regulatory authority.

In addition, all study treatments must be paused in any patient who experiences a TEAE meeting the DLT criteria regardless of when it occurs pending further evaluation by the Investigator and/or IDMC.

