# 6.11. Management of Atezolizumab-Related Toxicities

Atezolizumab-related toxicities should be managed according to recommendations provided in its label (TECENTRIQ PI, 2022) and IB v19. Recommended dose modifications for adverse reactions that are anticipated with the atezolizumab infusion are summarized in Table 2 and additional details are provided in

**Table 2:** Recommended Dosage Modifications for Adverse Reactions

Adverse Reaction	Severity a	Dosage Modification
Immune-Mediated Adverse Reactions [see V	Varnings and Precautions (5.1) Section	of TECENTRIQ PI]
Pneumonitis	Grade 1	Consider withholding
	Grade 2	Withhold b
	Grade 3 or 4	Permanently discontinue
Cardiac Events (Immune-mediated	Grade 2 to 4	Permanently discontinue
Myocarditis, Immune-mediated pericardial		
disorders)		
Colitis	Grade 2 or 3	Withhold
	Grade 4	Permanently discontinue
Dermatologic Events	Grade 3	Withhold
	Grade 4	Permanently discontinue
Endocrinopathies	Grade 2	Consider withholding
	Grades 3 or 4	Withhold until clinically
		stable or permanently
		discontinue depending on
		severity
Exfoliative Dermatologic Conditions	Suspected SJS, TEN, or DRESS	Withhold
	Confirmed SJS, TEN, or DRESS	Permanently discontinue
Hepatitis with no tumor involvement of the	AST or ALT increases to more	Withhold b
liver	than 3 and up to 5 times ULN or	
	Total bilirubin increases to more	
	than 1.5 and up to 3 times ULN	
	AST or ALT increases to more	Permanently discontinue
	than 5 times ULN or Total bilirubin	
	increases to more than 3 times	
	ULN	
Hepatitis with tumor involvement of the	Baseline AST or ALT is more than	Withhold b
liver c	1 and up to 3 times ULN and	

Adverse Reaction	Severity a	Dosage Modification
	increases to more than 5 and up to	
	10 times ULN or Baseline AST or	
	ALT is more than 3 and up to 5	
	times ULN and increases to more	
	than 8 and up to 10 times ULN	
	If ALT/AST increases to >10x	Permanently discontinue
	ULN or total bilirubin increases to	
	>3x ULN	
Hypophysitis	Grade 2 or 3	Withhold
	Grade 4	Permanently discontinue
Nephritis with Renal Dysfunction	Grade 2: (creatinine level > 1.5 to 3.0 x baseline or >1.5 to 3.0 x ULN)	Withhold b
	Grade 3 or 4: (creatinine level > 3.0 x baseline or >3.0 x ULN)	Permanently discontinue
Meningoencephalitis	All grades	Permanently discontinue
Myasthenic Syndrome/myasthenia gravis,	All Grades	Permanently discontinue
Guillain-Barré syndrome and		
Meningoencephalitis		

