#### 10.2. Evaluation and Classification

#### **10.2.1.** Evaluation of Severity

All AEs (including SAEs) are to be accurately recorded on the AE page of the patient's eCRF. Each event will be graded for severity using the classifications of NCI CTCAE v5.0 (NCI 2017).

For events not addressed in the NCI CTCAE v5.0 classifications, the following grading will apply:

- Mild (Grade 1) Mild; asymptomatic or mild symptoms; clinical or diagnostic observations only; intervention not indicated.
- Moderate (Grade 2) Moderate; minimal, local, or noninvasive intervention indicated; limiting age-appropriate instrumental activity of daily living.
- Severe (Grade 3) Severe or medically significant but not immediately life-threatening; hospitalization or prolongation of hospitalization indicated; disabling; limiting self-care activity of daily living.
- Life-threatening (Grade 4) Life-threatening consequences; urgent intervention indicated.
- Fatal (Grade 5) Related to AE.

During initial dosing and its respective post-observation period, any clinical finding despite its severity that represents a change from baseline (e.g., mild skin reaction, fatigue, myalgia, etc.) shall be recorded and followed until resolution.

Likewise, any clinically significant finding identified during the remaining course of the study, which represents a change from baseline would be required to be recorded by the Investigator.

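### The Section 6.10 liver stopping rule for AFM24 pairs the word 'severe' with a grade above 3, so for parts of the study the action for a Grade 3 liver event is unclear

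*Protocol*

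**What the plan says.** The hepatotoxicity paragraph of Protocol Section 6.10 reads: "If severe (>CTCAE Grade 3) hepatic impairment develops for patient with / without liver metastasis, AFM24 should be discontinued permanently".

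Two parts of the *Other* paragraph at the end of the same section bear on it. For Grade 3 toxicities that are not Phase 1 Cycle 1 DLTs, "and other than those described above, interrupt treatment with AFM24 until resolved to Grade ≤1 or baseline". And "in case of CTCAE Grade 4 toxicity, permanently discontinue treatment".

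Section 10.2.1 gives a verbal severity scale. One entry is "Severe (Grade 3) Severe or medically significant but not immediately life-threatening"; the next level up, Grade 4, is labelled life-threatening. The scale is introduced with a limit: "For events not addressed in the NCI CTCAE v5.0 classifications, the following grading will apply".

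For the expansion phase, Section 4.2.4 adds that "all study treatments must be paused in any patient who experiences a TEAE meeting the DLT criteria regardless of when it occurs", until the case has been evaluated.

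**The concern.** A stopping rule for a serious organ toxicity should lead every site to the same action for the same event. Here the word points to Grade 3 and the symbol points to Grade 4 or worse, and the *Other* paragraph does not clearly settle which rule a Grade 3 liver event falls under.

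Two things are at stake. The first is patient safety: EXP-3 enrols hepatocellular and hepatobiliary cancers, and the paragraph itself covers patients with liver metastases. The second is reporting. SAP Section 8.7.2 tabulates TEAEs leading to discontinuation and to interruption. With approximately 20 centers, the split between those two tables could partly reflect how each site reads one sentence.

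**Working it through.** The plan states no figure to reproduce and no arithmetic applies. The check sets the rules side by side.

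**Step 1: the sentence itself.** Above Grade 3, taken literally, means Grade 4 or higher. Section 10.2.1 attaches 'severe' to Grade 3. Both cannot define the same threshold.

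**Step 2: what Section 6.10 then requires for a Grade 3 liver event.**

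- (a) The word governs: permanent stop.
- (b) The symbol governs, and only liver events above Grade 3 count as already described: Grade 3 falls to *Other*, so interrupt until recovery, with rechallenge possible.
- (c) The symbol governs, and hepatotoxicity as a heading counts as already described: *Other* does not apply, so Section 6.10 mandates no AFM24 action.

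The general delay provision in Section 6.7 does not choose between these. It is permissive, and it is switched off during the DLT observation period.

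**Step 3: which readings survive in each part of the study.** Rules elsewhere close some of them. Table 1 in Section 4.2.3.1 lists "≥CTCAE Grade 3 total bilirubin" as a DLT criterion with no duration condition. Grade 3 or higher ALT, AST or alkaline phosphatase counts only if it does not resolve to Grade 1 or baseline within 10 days.

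| Setting | Rule outside the hepatotoxicity sentence | AFM24 readings left |
|---|---|---|
| Lead-in, possibly related, Grade 3 or higher | Permanent discontinuation (Synopsis, lead-in phase; SAP 4.2) | Settled |
| Phase 1 Cycle 1, liver event meeting DLT criteria | Permanent discontinuation (4.2.3.1; opening line of 6.10) | Settled |
| Phase 1 Cycle 1, Grade 3 ALT/AST/ALP resolving within 10 days | None mandatory | (a), (b), (c) |
| Phase 1 from Cycle 2 | None mandatory | (a), (b), (c) |
| Phase 2a, liver event meeting DLT criteria | Pause all study treatment (4.2.4) | (a) or (b) |
| Phase 2a, Grade 3 ALT/AST/ALP resolving within 10 days | None mandatory | (a), (b), (c) |

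Of the six settings, two are settled, one is narrowed to stop against interrupt-and-resume, and three are fully open. In Phase 2a the no-action reading is not available for Grade 3 bilirubin that meets the DLT definition.

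**The case against.** **The sign may be an extraction slip.** If the source prints 'at least Grade 3', word and grade agree, the *Other* carve-out works and the point falls away. The supplied text does vary in this way elsewhere: one 3+3 rule appears as more than 2 out of 3 in Section 4.2.3 and as at least 2 out of 3 in the Synopsis. Against that, the at-least sign survives in the skin and electrolyte paragraphs of Section 6.10 itself. The possibility stands and must be checked, but it is not shown.

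**A management summary is not visible.** Section 6.10 points to a summary for IRR/CRS and other AFM24-related events, and its target is not in the supplied text. It may state the Grade 3 liver action, so reading (c) is a statement about Section 6.10 as supplied, not about the whole plan. It would not make the word and the grade in this sentence agree.

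**The severity scale has limited scope.** Section 10.2.1 offers its labels only for events that CTCAE v5.0 does not grade, while Table 1 gives CTCAE grades for bilirubin and the liver enzymes. That is a fair limit. It is still the only meaning of 'severe' that the documents supply.

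**A coherent literal reading exists.** Reading (b) is consistent and may be what was meant. It makes the separate liver sentence largely repeat the Grade 4 rule in *Other*. That overlap is weak evidence, because a reader who excludes liver events from *Other* may exclude them from its Grade 4 clause too.

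**Stronger readings that the documents do not support.** A reader might infer that every Grade 3 liver event is open to three actions. The table shows otherwise. A reader might also take the atezolizumab liver limits in Table 2 as proof of conflict. Those rules govern another drug, use CTCAE version 4, and set different enzyme limits when the liver is involved and baseline values are raised. The Section 6.7 provision for continuing one component alone is also conditional, on investigator discretion and on the patient still meeting entry criteria. Table 2 therefore does not settle or contradict the AFM24 action.

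**Conclusion.** As printed, the word and the grade in the hepatotoxicity sentence disagree, and the *Other* paragraph leaves unclear whether a Grade 3 liver event means a permanent stop, an interruption or no mandated AFM24 action. This is a conflict in a safety threshold, worth correcting, with the limited reach shown above.

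The SAP (Sections 4.3 and 4.4) describes dose escalation as completed, so for new patients the exposure lies in Phase 2a, planned for up to 130. The documents give no rate of Grade 3 liver events. A reader might want to turn the 130 into a number of affected patients, but any such number would rest on an invented rate.

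The conclusion assumes that the sign is as printed, that the summary not supplied does not override the sentence, and that the 10-day condition in Table 1 keeps shorter enzyme rises outside the DLT criteria. No view is taken on which threshold or action is right.

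**What to change.** First check the sign in the hepatotoxicity sentence against the source PDF, and read the management summary that Section 6.10 points to. If the sign is in fact 'at least', no change is needed on this point.

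Otherwise reconcile the sentence with Section 10.2.1, the *Other* paragraph and the Section 4.2.4 pause rule, so that:

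- the word and the grade agree;
- Section 6.10 says whether *Other* applies to Grade 3 liver events;
- it is clear how the Phase 2a pause relates to the Section 6.10 action once the event has been evaluated.

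The sponsor's clinical team decides the threshold and the action.

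The cost is wording in one paragraph and a cross-reference, with no added patients or procedures. SAP Section 10 already mentions an upcoming protocol amendment, which could carry it.
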